We plan to enroll 90 participants. Eligibility and inclusion/exclusion criteria have been selected on the basis of efficacy endpoints and safety concerns and contraindications to scopolamine therapy or PET scanning to minimize the potential for adverse events. Recognized contraindications and medical conditions preventing the use of scopolamine patches or those requiring dosage adjustments will be screened for and subjects excluded from the protocol. Inclusion Criteria: 1. 65 years and older 2. Non-demented 3. No previous reaction or contraindication to scopolamine patch, or medical condition warranting dose adjustment in scopolamine including but not limited to: open angle glaucoma, gastrointestinal or urinary outlet obstructions, seizures, or psychosis. 4. No contraindications to A $\beta$ -PET scan including hypersensitivity to PET ligand or radiation exposures in the past year that would exceed the acceptable safe annual exposure in combination with the A $\beta$  PET 5. Medically stable and able to complete all study activities, as determined by the investigator 6. Reporting at least one potentially inappropriate medication as listed in the Beers 2015 criteria 7. Living in the community 8. Able to identify a study partner who will drive the participant to and from the scopolamine-challenged visits. 9. Willing to participate in this intervention study. Exclusion Criteria: 1. Allergy or other known intolerance to scopolamine patches 2. Narrow-angle glaucoma 3. Difficulty swallowing 4. Stomach or bowel problems (e.g., blockage, muscle weakness, ulcerative colitis) 5. Bleeding 6. Myasthenia gravis 7. Blockage of the urinary tract. 8. Seizures 9. Psychosis

Attachments

**Subject Recruitment Methods & Privacy:** Describe plans for the identification and recruitment of subjects, including how the population will be identified, and how initial contact will be made with potential subjects by those having legitimate access to the subjects’ identity and the subjects’ information. Describe the setting in which an individual will be interacting with an investigator. If applicable, describe proposed outreach programs for recruiting women and minorities as participants in clinical research.

Please note: Based upon both legal and ethical concerns, the UK Medical Institutional Review Board (IRB) will not approve finder’s fees for research studies.

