Screening Visit (Week -5 ± 2): Subject appropriateness and safety for the study will be assessed with thorough review of medical history, medication review, physical/neurological exam, vital signs, and ECG. SF-36 will assess pre- study perceived health status. Lifestyle Factor Questionnaire will further assess health history and current health status. A Baseline Questionnaire will assess motivation for participating and understanding of medications. Aβ-PET will be performed to allow stratification at baseline. Approximately 4 hours. Baseline and EOS visit (Scopolamine-challenge; week -4 ± 1 & week 52 ± 1): Subject will apply scopolamine patch at ~8pm the night before this visit to ensure adequate plasma levels of scopolamine. Study partner will drive subject to and from appointment. Medical history and medication review will be performed to ensure no changes have occurred since prior visit. Vital signs will be obtained. Cognitive testing including TMTB, MoCA, CVLT will be performed. Following cognitive testing, subject will remove scopolamine patch. Baseline and EOS visit (Non-challenge; week 0 ± 1 & week 56 ± 1): Medical history and medication review will be performed to ensure no changes have occurred since prior visit. Vital signs will be obtained. Cognitive testing including TMTB, MoCA, and CVLT will be performed. MTM intervention vs. placebo distribution of educational materials on PIM use will be performed. SF-36, Lifestyle Factors Questionnaire, and End of Study (EOS) Questionnaire will be administered at the EOS visit to assess changes in health status. Month 3 & 9 visits (week 13 ± 1 & week 39 ± 1): Telephone check to screen for adverse effects, update medical history and medication review. Month 6 visit (week 26 ± 1): Medical history and medication review will be performed to ensure no changes have occurred since prior visit. Vital signs will be obtained MTM intervention vs. placebo distribution of educational materials on PIM use will be performed. Randomization: For randomization, subjects will be stratified by Aβ positivity on PET scans; if age, gender, education, NART scores, and the number of targeted inappropriate medications using 2015 Beers Criteria are unbalanced between groups after randomization, they will be included in the analyses. Blinding: As the intervention is educational in nature, complete blinding of intervention is not possible. However, we will take the following steps in order to minimize potential bias and achieve the maximum level of blinding possible by this design: 1. When reviewing the medication list prior to the intervention, the coordinator, study pharmacist, and physician will be unaware of the group allocation. 2. Data analysis will be blinded to the intervention.

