Study Title: Intervention for Cognitive Reserve Enhancement in delaying the onset of Alzheimer's Symptomatic Expression (INCREASE) Study

ClinicalTrials.gov NCT02849639

Developed: December 14, 2015

Statistical analyses

We will use Student's t-tests (or Wilcoxon rank sum tests for non-normally distributed variables) and chi-square or Fisher's exact tests to assess the comparability of randomized study groups. To examine the effect of the intervention on prescribing appropriateness we will perform analysis of covariance (ANCOVA), with the dependent variables being the difference between MAI scores at baseline and the follow-up measure. We will control for any variables that might be significantly different between groups at baseline that have not already been included in the study protocol in regards to stratification of subjects.

Data evaluating cognitive reserve will be analyzed by intervention groups. For Aim 2, the impact on cognitive reserve will be assessed across the full range of SUVR (i.e., SUVR will be included in the analysis as continuous variable). If imbalance exists between groups after randomization, covariates for analysis will include age, gender, education, NART scores, and the number of targeted inappropriate medications using 2015 Beers Criteria. We will investigate change from baseline in CRCS by group using ANCOVA.

For the perceived health status measure, because the SF-36 does not produce a single overall measure and because of our concern regarding multiple comparisons, multivariate analysis of covariance (MANCOVA) will be used to simultaneously estimate the effect of the intervention on the eight SF-36 health concepts. Similarly, we will also control for any variables that might be significantly different between groups at baseline.

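### The SAP leaves the SF-36 outcome form undefined and uses the screening SF-36 at most conditionally on a baseline significance test; the screening scores should always be covariates.

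*SAP*

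**What the plan says.** The protocol's Research Procedures section collects the questionnaire twice. At the screening visit, "SF-36 will assess pre- study perceived health status". At the end of the trial it "will be administered at the EOS visit to assess changes in health status".

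The SAP (Statistical analyses, last paragraph) specifies the model: "multivariate analysis of covariance (MANCOVA) will be used to simultaneously estimate the effect of the intervention on the eight SF-36 health concepts". It then adds the covariate rule: "Similarly, we will also control for any variables that might be significantly different between groups at baseline".

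The same SAP section is explicit about the outcome form for the other two measures. The MAI analysis is an ANCOVA "with the dependent variables being the difference between MAI scores at baseline and the follow-up measure". For cognitive reserve, "We will investigate change from baseline in CRCS by group using ANCOVA". The SF-36 sentence has no such phrase. Neither document names the screening SF-36 as a planned covariate. The conditional covariates that are listed (age, gender, education, NART and number of targeted inappropriate medications) do not include it.

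**The concern.** Two things are left open. The first is the outcome: an end-of-study score and a change score are both compatible with the text, and they have different precision. Leaving the choice until the data are in hand is avoidable.

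The second is the baseline score. A participant's screening score would normally be expected to predict the same person's later score, and here it is already collected. The plan uses it only if a significance test between randomised arms happens to flag it. Such a test says nothing about whether a variable predicts the outcome. With two randomised arms it flags a given domain about one time in twenty, so the covariate is nearly always left out.

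If end-of-study scores are analysed, the stakes are wider standard errors on all eight domains, a weaker joint test, and chance baseline differences that pass into the estimate in the realised trial. If unadjusted change is analysed, precision depends heavily on the correlation between the two visits and can be worse than using end-of-study scores alone.

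**Working it through.** The documents give no power, effect size, SD or correlation for the SF-36, so there is no figure of the plan's own to reproduce.

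**Inputs.** Total sample: "We plan to enroll 90 participants" (Protocol, Study Population). Assumed, because the documents do not state them: 1:1 allocation (45 per arm), no dropout, two-sided 5% level, equal SDs at the two visits, and a correlation ρ of 0.3 to 0.7 between screening and end-of-study scores.

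**1. How often the rule acts, and what it misses.** The SE of a baseline difference is √(2/45) = 0.211 SD. The 5% threshold is about 1.99 × 0.211 = 0.42 SD. A given domain crosses it by chance in about 5% of trials. If the eight domains were independent, at least one would cross in 1 − 0.95⁸ = 34% of trials, and in fewer if they are positively correlated. In an end-of-study contrast, a baseline difference b carries ρ × b into the estimate:
- just below the threshold: 0.5 × 0.42 = 0.21 SD to 0.7 × 0.42 = 0.29 SD
- a more typical imbalance of one SE: 0.5 × 0.211 = 0.11 SD to 0.7 × 0.211 = 0.15 SD

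**2. Precision, one domain at a time.** Variance of the group difference relative to end-of-study scores alone is 1 − ρ² with baseline adjustment and 2(1 − ρ) for unadjusted change. The conditional rule and its always-adjust comparator were simulated with 20,000 runs at ρ = 0.5 and 0.7.

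| ρ | Always adjust, 1 − ρ² | Always adjust, simulated | Conditional rule, simulated | Unadjusted change, 2(1 − ρ) |
|---|---|---|---|---|
| 0.3 | 0.91 | – | – | 1.40 |
| 0.5 | 0.75 | 0.77 | 0.94 | 1.00 |
| 0.7 | 0.51 | 0.52 | 0.87 | 0.60 |

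The conditional rule recovers only a small part of the available gain. Unadjusted change beats end-of-study scores only when ρ exceeds 0.5.

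**3. Power of the joint test.** Further assumptions: a 0.4 SD benefit in every domain and inter-domain correlation 0.5.
- Squared multivariate distance: 8 × 0.4² / (1 + 7 × 0.5) = 1.28/4.5 = 0.284.
- Noncentrality for end-of-study scores: (45/2) × 0.284 = 6.4, with F on 8 and 90 − 8 − 1 = 81 df.
- For unadjusted change, divide 6.4 by 2(1 − ρ).
- With eight screening covariates, divide 6.4 by 1 − ρ². Then allow for chance imbalance in eight covariates, which inflates the variance of the adjusted difference by an average of (90 − 3)/(90 − 8 − 3) = 87/79 = 1.10. The test uses F on 8 and 73 df.

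| ρ | End-of-study only | Unadjusted change | Screening scores always in | Noncentrality, last column |
|---|---|---|---|---|
| 0.3 | 35% | 25% | 34% | 6.4/0.91/1.10 = 6.4 |
| 0.5 | 35% | 35% | 42% | 6.4/0.75/1.10 = 7.7 |
| 0.6 | 35% | 43% | 49% | 6.4/0.64/1.10 = 9.1 |
| 0.7 | 35% | 57% | 60% | 6.4/0.51/1.10 = 11.4 |

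Direct simulation of the three analyses agrees to within about one percentage point. The 1.10 factor matters: reducing the error df without it would overstate the adjusted power as 46%, 54% and 65% at ρ of 0.5, 0.6 and 0.7.

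**4. Missing domains.** A complete-case MANCOVA needs all eight end-of-study scores. If each domain were missing independently in 1% to 3% of forms, the loss would be 1 − 0.99⁸ = 8% to 1 − 0.97⁸ = 22%. Requiring eight screening scores as well would raise it to 1 − 0.99¹⁶ = 15% to 1 − 0.97¹⁶ = 39%. These are upper bounds, because missing items tend to fall in the same forms. They show that baseline adjustment needs a rule for missing screening domains.

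**The case against.** A reader might infer that the MANCOVA compares end-of-study scores only and ignores the screening SF-36. The documents do not support that. The dependent variable is simply not defined, and the protocol's stated purpose for the second questionnaire is to assess change. The MAI and CRCS analyses are both on change, so a change analysis is a plausible reading. Nor is the screening SF-36 excluded: a domain that differed significantly at baseline would be adjusted for.

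It would also be too strong to say that the SF-36 comparison is biased. Randomisation keeps even an unadjusted contrast unbiased on average. The carry-over shown above is an error conditional on the imbalance that occurs, and the 0.21 to 0.29 SD figures are the extreme just below the threshold.

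If change scores are intended, the benefit of adjustment is smaller: about 7, 6 and 3 percentage points of power at ρ of 0.5, 0.6 and 0.7 (42 − 35, 49 − 43, 60 − 57). If ρ is near 0.3, adjustment gains nothing over end-of-study scores. Finally, the primary outcomes in the protocol's Objectives are MAI and CRCS, and the SF-36 appears in neither aim.

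All of this stands, and it narrows the point. It does not supply the missing outcome definition, and it does not make the significance-test rule a good way to use a baseline that has already been collected.

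**Conclusion.** The point holds in limited form. The SAP does not say which SF-36 quantity is analysed, and it uses the screening scores only when a baseline test flags them. That leaves relative variance at about 0.94 (ρ = 0.5) or 0.87 (ρ = 0.7), where routine adjustment would give 0.77 or 0.52. In the joint-test illustration, routine adjustment has the highest power of the three analyses for ρ from 0.5 to 0.7. Its advantage over end-of-study scores is about 7 to 25 percentage points (42 − 35 to 60 − 35). Clarifying the text to unadjusted change would not be enough, since that is worse than end-of-study scores when ρ is below 0.5.

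These sizes rest on assumed correlations, a uniform 0.4 SD effect, 45 per arm and complete data. The wording gap does not depend on them. No conclusion on a primary outcome is affected. The change is worth making because it needs no new data and settles the analysis in advance.

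**What to change.** Replace the SF-36 model and covariate sentences with wording along these lines: *The eight end-of-study SF-36 domain scores will be analysed jointly by randomised group using MANCOVA. The eight screening SF-36 domain scores will always be included as covariates, whether or not they differ between groups. A missing screening domain score will be replaced by the mean of the observed screening scores for that domain, pooled over both groups, so that no participant is lost for a missing baseline value.* Also state how incomplete end-of-study forms will be handled.

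The cost is SAP text and 8 error degrees of freedom (81 to 73 in the joint test), plus the roughly 10% variance inflation already counted above. Both questionnaires are already scheduled. With the imputation rule, complete-case loss stays at whatever the end-of-study forms produce. A joint mixed model of both visits would also keep partly completed forms. However, an unstructured covariance for 16 scores has 16 × 17/2 = 136 parameters for 90 participants, so it is not the simpler option here.
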